6.5.6. Tuberculosis

After an extensive clinical development program, there is no current evidence that apremilast has the potential to activate latent TB. Therefore, no TB testing will be done in this protocol. Investigators can test for TB if clinically indicated, using the site's local or country-specific guidelines. If the subject has active or latent TB, he/she should be treated according to local guidelines. Subjects who require TB treatment at any time during the study must be discontinued.

6.5.7. Clinical Laboratory Evaluations

Clinical laboratory evaluations will be performed by the central laboratory as indicated in Table 13, Table of Events. These include complete blood count (red blood cell [RBC] count, hemoglobin, hematocrit, white blood cell [WBC] count and differential, absolute WBC counts, platelet count) and serum chemistries (total protein, albumin, calcium, phosphorous, glucose, triglycerides, total cholesterol [TC], total bilirubin, alkaline phosphatase, aspartate aminotransferase [AST; serum glutamic-oxaloacetic transaminase, SGOT], alanine aminotransferase [ALT; serum glutamic pyruvic transaminase, SGPT], sodium, potassium, chloride, bicarbonate [carbon dioxide, CO₂], blood urea nitrogen, creatinine, creatinine clearance [estimated by the Cockcroft–Gault equation], lactate dehydrogenase [LDH], and magnesium); rheumatoid factor; high-sensitivity C-reactive protein (hsCRP), urinalysis (specific gravity, pH, glucose, ketones, protein, blood, bilirubin, leukocyte esterase, nitrite, and urobilinogen. Microscopic urinalysis (epithelial cells, red blood cells [RBCs], white blood cells [WBCs], crystals, bacteria, and casts) will be performed only if the urinalysis is abnormal.

6.5.8. Adverse Events

All subjects will be monitored for adverse events (AEs) during the study. Assessments may include monitoring of any or all of the following parameters: the subject's clinical symptoms, laboratory, pathological, radiological, or surgical findings; physical examination findings; or other appropriate tests and procedures.

All AEs will be recorded by the Investigator from the time the subject signs informed consent to 28 days after the last dose of IP. Adverse events and serious adverse events (SAEs) will be recorded on the AE page of the electronic case report form (eCRF), the paper SAE reporting form (SAEs) and in the subject's source documents. All SAEs must be reported to Amgen Global Patient Safety immediately (ie, within 24 hours of the Investigator's knowledge of the event) by recording on the CRF and completing the paper SAE Report Form which is sent directly to Amgen Global Patient Safety by facsimile or email.

[figure not shown]
Details of AE reporting can be found in Section 10 of the protocol. It should be noted that worsening of a subject's psoriatic arthritis should be considered as worsening of disease under study and should not be captured as an adverse event.

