6.5.3. Complete/Limited Physical Examination

A complete physical examination includes evaluations of skin, nasal cavities, eyes, ears, lymph nodes, and respiratory, cardiovascular, gastrointestinal, neurological, and musculoskeletal (assessment of joints and spine) systems. A complete physical examination is done at Screening and other designated visits as indicated in Table 13, Table of Events. A limited physical examination includes evaluations of skin, lymph nodes, and respiratory, cardiovascular, and

musculoskeletal systems. A limited physical examination is done at the Baseline Visit and other designated visits as indicated in Table 13.

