10. ADVERSE EVENTS

10.1. Monitoring, Recording and Reporting of Adverse Events

An AE is any noxious, unintended, or untoward medical occurrence that may appear or worsen in a subject during the course of a study. It may be a new intercurrent illness, a worsening concomitant illness, an injury, or any concomitant impairment of the subject's health, including laboratory test values (as specified by the criteria in Section 10.3), regardless of etiology. Any worsening (ie, any clinically significant adverse change in the frequency or intensity of a preexisting condition) should be considered an AE. A diagnosis or syndrome should be recorded on the AE/SAE page of the CRF rather than the individual signs or symptoms of the diagnosis or syndrome.

Abuse, withdrawal, sensitivity or toxicity to an investigational product should be reported as an AE. Overdose, accidental or intentional, whether or not it is associated with an AE should be reported on the overdose CRF. (See Section 7.8 for the definition of overdose.) Any sequela of an accidental or intentional overdose of an investigational product which meets the definition of an adverse event, should be reported as an AE on the CRF. If the sequela of an overdose meets serious criteria, then it must be marked as serious on the CRF, and the paper SAE Report form. The overdose itself should not be reported as an AE.

In the event of overdose, the subject should be monitored as appropriate and should receive supportive measures as necessary. There is no known specific antidote for apremilast overdose. Actual treatment should depend on the severity of the clinical situation and the judgment and experience of the treating physician.

All subjects will be monitored for AEs during the study. Assessments may include monitoring of any or all of the following parameters: the subject's clinical symptoms, laboratory, pathological, radiological or surgical findings, physical examination findings, or findings from other tests and/or procedures.

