10.2.1. Seriousness

An SAE is any AE occurring at any dose that:

- Results in death;
- Is life-threatening (ie, in the opinion of the Investigator, the subject is at immediate risk of death from the AE);
- Requires inpatient hospitalization or prolongation of existing hospitalization (hospitalization is defined as an inpatient admission, regardless of length of stay);
- Results in persistent or significant disability/incapacity (a substantial disruption of the subject's ability to conduct normal life functions);
- Is a congenital anomaly/birth defect;
- Constitutes an important medical event.

Important medical events are defined as those occurrences that may not be immediately life-threatening or result in death, hospitalization, or disability, but may jeopardize the subject or require medical or surgical intervention to prevent one of the other outcomes listed above. Medical and scientific judgment should be exercised in deciding whether such an AE should be considered serious.

Events not considered to be SAEs are hospitalizations for:

- A standard procedure for protocol therapy administration. However, hospitalization or prolonged hospitalization for a complication of therapy administration will be reported as an SAE.
- Routine treatment or monitoring of the studied indication not associated with any deterioration in condition.
- The administration of blood or platelet transfusion as routine treatment of studied indication. However, hospitalization or prolonged hospitalization for a complication of such transfusion remains a reportable SAE.
- A procedure for protocol/disease-related investigations (eg, surgery, scans, endoscopy, sampling for laboratory tests, bone marrow sampling). However, hospitalization or prolonged hospitalization for a complication of such procedures remains a reportable SAE.
- Hospitalization or prolongation of hospitalization for technical, practical, or social reasons, in absence of an AE.
- A procedure that is planned (ie, planned prior to start of treatment on study); must be documented in the source document and the CRF. Hospitalization or prolonged hospitalization for a complication remains a reportable SAE.
- An elective treatment of or an elective procedure for a pre-existing condition, unrelated to the studied indication, that has not worsened from baseline.
- Emergency outpatient treatment or observation that does not result in admission, unless fulfilling other seriousness criteria above.

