10.5. Reporting of Serious Adverse Events

Any AE that meets any seriousness criterion for an SAE requires the reporting of an SAE within 24 hours of the Investigator's knowledge of the event. This instruction pertains to initial SAE reports as well as any follow-up reports.

This requirement applies to all SAEs (regardless of relationship to IP) that occur during the study (from the time the subject signs informed consent until 28 days after the last dose of IP) and any SAE made known to the Investigator at any time following the protocol-required reporting

period or after end of study. Serious adverse events occurring prior to treatment (after signing the ICF) are to be collected/recorded/reported.

Where required by local legislation, the Investigator is responsible for informing the Institutional Review Board/Ethics Committee (IRB/EC) of the SAE and providing them with all relevant initial and follow-up information about the event. The Investigator must keep copies of all SAE information on file including correspondence with Amgen and the IRB/EC.

The SAE is recorded within the CRF and reported directly to Amgen Global Patient Safety by facsimile, email, or other appropriate method within 24 hours of the Investigator's knowledge of the event, using the paper SAE Report form.

Where required by local legislation, the Investigator is responsible for informing the Institutional Review Board/Ethics Committee (IRB/EC) of the SAE and providing them with all relevant initial and follow-up information about the event. The Investigator must keep copies of all SAE information on file including correspondence with Amgen and the IRB/EC.

Serious Adverse Event Reporting Transmitted Via Paper Serious Adverse Event Report Form:

- Facsimile transmission of the SAE Report Form is the preferred method to transmit this information. If facsimile is unavailable, the email method to transmit this information is acceptable (refer to Appendix W).
- In rare circumstances and in the absence of facsimile equipment, this form may be sent via email, or notification by telephone is acceptable with a copy of the Serious Adverse Event Report Form in English language sent by overnight mail or courier service.
- Initial notification via telephone does not replace the need for the investigator to complete and sign the SAE Report Form within the designated reporting timeframes.

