#### 9.6.6 Physical Measurements

Physical examination findings will be captured as medical history at screening. Abnormal physical examination findings post Screening will be reported as adverse events and will be reported in the summaries.

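### Protocol 6.5.8 keeps worsening of psoriatic arthritis out of adverse event capture with no exception for serious events, so whether a serious flare is reported depends on whether 6.5.8 or Section 10 is followed.

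*Protocol*

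**What the plan says.** Four parts of the protocol bear on how worsening PsA is recorded.

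- **6.5.8 (Adverse Events).** It first sends the reader elsewhere: "Details of AE reporting can be found in Section 10 of the protocol". It then adds a note that "worsening of a subject's psoriatic arthritis should be considered as worsening of disease under study and should not be captured as an adverse event". The note has no qualifier for seriousness or for suspected relation to study drug.
- **10.1 (Monitoring, Recording and Reporting).** "Any worsening (ie, any clinically significant adverse change in the frequency or intensity of a preexisting condition) should be considered an AE". Section 10 does not repeat the PsA exclusion.
- **10.2.1 (Seriousness).** The definition opens "An SAE is any AE occurring at any dose that" and then lists the criteria, inpatient admission among them. A second list gives hospitalisations that are not SAEs. One entry reads "Routine treatment or monitoring of the studied indication not associated with any deterioration in condition".
- **10.5 (Reporting of SAEs).** "Any AE that meets any seriousness criterion for an SAE requires the reporting of an SAE within 24 hours".

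The SAP has a related statement in 9.6.6: "Abnormal physical examination findings post Screening will be reported as adverse events and will be reported in the summaries". Protocol 6.5.3 includes in the complete examination the "musculoskeletal (assessment of joints and spine) systems". SAP 9.6.2, which lists the AE summaries, has no rule for identifying or separating PsA-worsening terms.

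**The concern.** Keeping ordinary worsening of the studied disease out of AE counts is a common and defensible choice, because the efficacy assessments already measure it. The difficulty is that 6.5.8 applies the exclusion to all worsening, serious cases included, and that Section 10, to which 6.5.8 refers for reporting details, contains no such exclusion.

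Safety reporting is what is at stake. If a subject is admitted with a PsA flare and the site follows 6.5.8 literally, there is no AE record. The event then gets no causality assessment under 10.2.3 and no 24-hour report under 10.5, and it does not reach the sponsor's judgement of expectedness under 10.6. A site following Section 10 would do all of these for the same admission. Whether a serious event reaches the sponsor should not turn on which section the site has read.

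**Working it through.** No arithmetic applies. The check is to take one event through each rule.

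**Test event:** a subject on treatment has a clinically significant flare of PsA and is admitted as an inpatient because of it.

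| Step | Following 6.5.8 | Following Section 10 |
|---|---|---|
| Is it an AE? | No. PsA worsening is not captured. | Yes. PsA is a preexisting condition in every subject (inclusion criteria 4 and 5), and 10.1 has no exception for it. |
| Does it meet a seriousness criterion? | Not reached, because 10.2.1 starts from an AE. | Yes, inpatient admission. |
| Does the 10.2.1 list of non-SAE hospitalisations remove it? | Not reached. | No. The entry for the studied indication is limited to admissions without deterioration. |
| 24-hour report under 10.5? | No, because the trigger is an AE. | Yes. |

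The outcomes are opposite, and they diverge at the first step. Sections 10.2.1 and 10.5 both depend on AE status, so neither can bring back an event that 6.5.8 has already excluded.

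**A non-serious flare.** The two columns again differ at the first step, but the consequence is smaller. No expedited report is involved, and the worsening is still recorded in the joint counts, visual analogue scales, HAQ-DI, enthesitis index and BSA collected at each treatment-phase visit (Table 13).

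**The primary endpoint.** Protocol 9.6.3 and SAP 9.5.1 set subjects who discontinue before Week 16 for either lack of efficacy or adverse event to non-response. A withdrawal prompted by a flare therefore gives the same Week 16 result under either label.

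**Size.** The nearest figures are in protocol 1.2.1.2.1. Over the first 16 weeks of exposure, serious treatment-emergent events of all kinds occurred in 22 of 671 placebo subjects (22/671 = 3.3%) and 44 of 1945 apremilast subjects (44/1945 = 2.3%). These cover all causes, pool the 20 mg and 30 mg groups, and come from trials requiring at least 3 swollen and 3 tender joints. They suggest that serious events are uncommon in this setting. They do not give a rate of serious PsA flares in subjects with 2 to 4 swollen and 2 to 4 tender joints, and no other figure in the documents does.

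**The case against.** The strongest reply is that the specific rule displaces the general one. In 6.5.8 the PsA sentence follows directly after the pointer to Section 10 and reads as a study-specific note on it. Section 10.1 is generic text that does not mention PsA. On that reading sites have a single rule. For non-serious worsening this is plausible, and the exclusion is sound in substance: it avoids counting loss of efficacy a second time as harm. That part of the objection stands.

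It does not settle serious worsening. If 6.5.8 prevails, it prevails for admissions too, since it has no limit, and serious flares then go unreported by rule. If it was not meant to reach that far, the protocol does not say so. Section 10.2.1 gives a contrary signal, because its exemption for the studied indication would not need the condition about deterioration if every PsA worsening were already outside AE capture.

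That signal is an inference. Section 10.2.1 lists what is not an SAE; it does not declare a hospitalised flare to be one. The list is also generic, with entries on platelet transfusion and bone marrow sampling, so it is weak evidence of a considered PsA rule. SAP 9.6.6 is weaker still: it describes how examination findings are reported and does not instruct sites on disease worsening. The conflict between 6.5.8 and 10.1 does not need either of them.

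A reader might go further and infer that overall AE rates, or the comparison of AEs and AE discontinuations between arms, will be distorted because flares should be commoner on placebo. The documents do not support that as a finding. They give no flare rate, the carve-out reading may well be what sites apply to non-serious events, lack of efficacy is a separate discontinuation reason in 11.1, and SAP 9.6.1 makes the safety analysis descriptive, with no formal test.

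**Conclusion.** The point holds for worsening that meets a seriousness criterion. Read literally, 6.5.8 keeps such an event out of AE capture and so out of 24-hour reporting, while Section 10 requires the report. This is an inconsistency in the current protocol text, and it should be corrected.

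The number of events is probably small. That is a judgement from the low all-cause serious event rates in the earlier pooled trials and not a calculation. Any effect on AE incidence, on exposure-adjusted rates or on the difference between arms cannot be quantified from the documents and is not claimed. The primary endpoint is unaffected by how a withdrawal before Week 16 is coded between adverse event and lack of efficacy.

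The conclusion assumes that sites have no instruction outside these documents, such as form completion guidelines, that already resolves the matter. It would be wrong to infer that serious flares are certain to be missed: 6.5.8 says they should not be captured, but a site that works from Section 10 would report them.

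**What to change.** Reconcile 6.5.8, 10.1 and 10.2.1 into one reporting rule:

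- In 6.5.8, keep the exclusion but limit it: worsening of PsA that meets no seriousness criterion in 10.2.1 is not captured as an AE; worsening that meets one is recorded as an AE and reported as an SAE under 10.5.
- In 10.1, add the matching exception for non-serious PsA worsening, with a cross-reference to 6.5.8.
- In 10.2.1, say that admission for deteriorating PsA is not among the exempt hospitalisations.

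SAP 9.6.6 should be read in line with the same rule. If sites have already worked to different readings, the SAP could show treatment-emergent events with and without PsA-worsening terms, so that the reader can see whether it matters.

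The wording is short, but the step is a protocol amendment. Section 13.5 requires written IRB/EC approval before implementation unless a change is administrative, and a change to SAE reporting is unlikely to qualify as that. The continuing cost is a few more SAE reports.

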6.6. Patient Reported Outcomes or Quality of Life or Health Economics

Questionnaires will be performed and as indicated in Table 13, Table of Events.

6.6.1. The PsA Impact of Disease 12-Item (PsAID-12) Questionnaire

The PsAID-12 Questionnaire (Appendix N; Gossec, 2014) is a 12-item, self-administered questionnaire that reflects the impact of PsA from the perspective of the patient. It is composed of 12 physical and psychological domains. Each domain is rated from 0 to 10 with a different weighting. The total score is divided by 20. The final score has a range from 0 (best status) to 10 (worst status) with a cut-off ≤ 4 .

7. DESCRIPTION OF STUDY TREATMENTS

7.1. Description of Investigational Product(s)

The chemical name of apremilast (CC-10004) is N-[2-[(1S)-1-(3-ethoxy-4-methoxyphenyl)-2-(methylsulfonyl)ethyl]-2,3-dihydro-1,3-dioxo-1H-isoindol-4-yl] acetamide.

Apremilast and placebo will be provided as identically appearing by the Sponsor and labeled appropriately as investigational product for this study. In addition, tablets (both apremilast and placebo) required for dose titration cards will also be provided.

Please refer to the IB for more details on approved indications, known precautions, warnings, and adverse reactions of apremilast.

The apremilast dosing schedule to be followed for this study is described in Section 7.2.

Additional information may be included on the label as needed or applicable. Label(s) for IP will contain information as required per local health authority.

7.2. Treatment Administration and Schedule

Tablets will be taken by mouth twice daily, in the morning (AM) and in the evening (PM), approximately 12 hours apart, with no food restrictions. To mitigate potential gastrointestinal (GI) adverse events, dose titration shall be implemented over a 5-day period (see Table 14).

At the Week 0 (ie, initial randomization), Week 16 (ie, for Early Escape subjects), and Week 24 (ie, Active-treatment Phase) visits, subjects will be dispensed blister cards with 10, 20, and 30 mg apremilast tablets or identically appearing placebo for the dose titration. Subjects will be dispensed blister cards containing 30 mg apremilast tablets or identically appearing placebo at designated visits (Table 13). Beginning at the Week 28 Visit, subjects will be dispensed open label bottles with 30 mg apremilast tablets. Pictures of the blister card configurations are shown in Appendix T. Dose modifications are not permissible in this study. Apremilast and placebo tablets (oral IP) are identical in appearance.

Table 14: Treatment of Schema for Dose Titration at Baseline

Dose	Day 1		Da	y 2	Da	y 3	Da	y 4	Day 5	
Group	AM	PM	AM	PM	AM	PM	AM	PM	AM	PM
Placebo (dummy titration)	10 mg placebo + 20 mg placebo + 30 mg placebo	10 mg placebo + 20 mg placebo + 30 mg placebo	10 mg placebo + 20 mg placebo + 30 mg placebo	10 mg placebo + 20 mg placebo + 30 mg placebo	10 mg placebo + 20 mg placebo + 30 mg placebo	10 mg placebo + 20 mg placebo + 30 mg placebo	10 mg placebo + 20 mg placebo + 30 mg placebo	10 mg placebo + 20 mg placebo + 30 mg placebo	10 mg placebo + 20 mg placebo + 30 mg placebo	10 mg placebo + 20 mg placebo + 30 mg placebo
30 mg apremilast (titration)	10 mg apremilast + 20 mg placebo + 30 mg placebo	10 mg placebo + 20 mg placebo + 30 mg placebo	10 mg apremilast + 20 mg placebo + 30 mg placebo	10 mg apremilast + 20 mg placebo + 30 mg placebo	10 mg apremilast + 20 mg placebo + 30 mg placebo	10 mg placebo + 20 mg apremilast + 30 mg placebo	10 mg placebo + 20 mg apremilast + 30 mg placebo	10 mg placebo + 20 mg apremilast + 30 mg placebo	10 mg placebo + 20 mg apremilast + 30 mg placebo	10 mg placebo + 20 mg placebo + 30 mg apremilast

Table 15: Treatment Schema for Dose Titration at Week 16 (Early Escape) or Week 24

Dose	Day 1		Day 2		Da	y 3	Da	y 4	Day 5	
Group	AM	PM	AM	PM	AM	PM	AM	PM	AM	PM
Placebo to 30 mg apremilast (titration)	10 mg apremilast + 20 mg placebo + 30 mg placebo	10 mg placebo + 20 mg placebo + 30 mg placebo	10 mg apremilast + 20 mg placebo + 30 mg placebo	10 mg apremilast + 20 mg placebo + 30 mg placebo	10 mg apremilast + 20 mg placebo + 30 mg placebo	10 mg placebo + 20 mg apremilast + 30 mg placebo	10 mg placebo + 20 mg apremilast + 30 mg placebo	+ 20 mg apremilast +	10 mg placebo + 20 mg apremilast + 30 mg placebo	10 mg placebo + 20 mg placebo + 30 mg apremilast
30 mg apremilast (dummy titration)	10 mg placebo + 20 mg placebo + 30 mg apremilast	10 mg placebo + 20 mg placebo + 30 mg apremilast	10 mg placebo + 20 mg placebo + 30 mg apremilast	10 mg placebo + 20 mg placebo + 30 mg apremilast	10 mg placebo + 20 mg placebo + 30 mg apremilast	10 mg placebo + 20 mg placebo + 30 mg apremilast	10 mg placebo + 20 mg placebo + 30 mg apremilast			

